8.3 Dose Delay Criteria Ipilimumab (Arm 1)

Dose modifications for ipilimumab by adverse event type are detailed in [Table 8.1](#). General considerations for dose modifications are as follows.

- a. It is necessary to avoid study drug dosing and initiate appropriate evaluation and/or treatment for the following adverse events:
- Any \geq Grade 3 skin related adverse event regardless of causality.
 - Any \geq Grade 2 non-skin related adverse event (including immune-mediated adverse reactions), except for easily corrected laboratory abnormalities that do not reflect underlying organ pathology.
 - Any \geq Grade 3 laboratory abnormality.
 - Any adverse event, laboratory abnormality or intercurrent illness that, in the opinion of the treating investigator, presents a substantial clinical risk to the patient with continued dosing.
 - It may be necessary to hold study drug to evaluate Grade 1 events that suggest ongoing or incipient autoimmune disease including GI toxicity, diarrhea, pancreatitis, hepatitis, pituitary insufficiency, early evidence of neurologic events, skin toxicity until diagnosis and progression are determined.
- b. Ipilimumab may be restarted if/when the adverse event(s) resolve(s) in severity or returns to baseline within 2 weeks of initial dose administration:
- If the adverse event has been determined not be related to ipilimumab or is not an autoimmune/inflammatory event. If more than 1 dose is to be skipped or > 2 week delay is expected due to current events not related to study the dosing schedule modifications must be discussed with the study chairs prior to implementation.
 - If the *adverse event has resolved to \leq Grade 1*, ipilimumab dosing may be restarted at the next scheduled timepoint per protocol. Please follow guidelines for specific events. Please note that re-initiating treatment may be associated with recurrence or exacerbation of autoimmune or inflammatory events. In some instances clinical resolution of events such as colitis may be associated with residual pathologic changes and should require evaluation of complete resolution prior to restarting therapy.
 - If the adverse event has not resolved in the protocol-specified dosing window (3 weeks [± 3 calendar days]), the next scheduled dose will be skipped and dosing will be resumed at the subsequently scheduled dose.

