 - Events which require intervention with immunosuppressant therapy, steroids, surgery, or hormone replacement generally require permanently stopping study treatment.
- c. Permanently discontinue ipilimumab for any of the following:
- Persistent adverse reactions that require holding more than 2 treatment doses.
 - Any related Grade 3 or 4 event (see exceptions below)
 - Any event that requires immunosuppressive treatment or systemic steroids which cannot be discontinued during the time in which it takes to hold more than 2 treatment doses
 - Severe or life-threatening adverse reactions, including any of the following:
 - Colitis with abdominal pain, fever, ileus, or peritoneal signs; increase in stool frequency (7 or more over baseline), stool incontinence, need for IV hydration for more than 24 hours, gastrointestinal hemorrhage, and gastrointestinal perforation

- Aspartate aminotransferase (AST) or alanine aminotransferase (ALT) >5 times the upper limit of normal or total bilirubin >3 times the upper limit of normal
- Stevens-Johnson syndrome, toxic epidermal necrolysis, or rash complicated by full thickness dermal ulceration, or necrotic, bullous, or hemorrhagic manifestations
- Severe motor or sensory neuropathy, Guillain-Barré syndrome, or myasthenia gravis
- Severe immune-mediated reactions involving any organ system (e.g., nephritis, pneumonitis, pancreatitis, non-infectious myocarditis)
- Immune-mediated ocular disease that is unresponsive to topical immunosuppressive therapy
- Any adverse event, laboratory abnormality or intercurrent illness which, in the judgment of the investigator, presents organ specific injury and/or a substantial clinical risk to the patient with continued dosing.

NOTE: The following neurological adverse events require permanent discontinuation of ipilimumab and define unacceptable neurotoxicity:

- Any motor neurologic toxicity \geq Grade 3 regardless of causality
- Any \geq Grade 3 treatment related sensory neurologic toxicity

Please refer to [Appendix 18.3](#) and [Appendix 18.4](#) for specific treatment algorithms.

- d. Exceptions to Permanent Discontinuation of Ipilimumab
- Potentially reversible inflammation (< Grade 4), attributable to a local anti-tumor reaction and a potential therapeutic response. This includes inflammatory reactions at sites of tumor resections or in draining lymph nodes, or at sites suspicious for, but not diagnostic of metastasis.

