8.4 Dose Delay Criteria for Nivolumab in Combination with Ipilimumab (Arm 2)

Dose modifications for nivolumab in combination with ipilimumab by adverse event type are detailed in [Table 8.1](#). General considerations for dose modifications are as follows.

For the initial induction period, patients with Grade 2 or 3 events requiring discontinuation of treatment with the combination may consider continuing treatment with single agent nivolumab when the event resolves to baseline. However, patients with renal, CNS, or pulmonary toxicity must be removed from study.

- a. In addition to the AEs identified in the table below, ipilimumab and nivolumab dose should be delayed for any AE, laboratory abnormality or inter-current illness which, in the judgment of the treating investigator, warrants delaying the dose of study medication.
- b. Patients requiring a delay of > 6 weeks or who experience immune-related toxicity with inability to decrease prednisone ≤ 10 mg PO daily must go off protocol therapy entirely.
- c. Patients who received systemic corticosteroids for management of any drug-related immunologic toxicity must be off corticosteroids or have tapered down to an equivalent dose of prednisone 10 mg/day.
- d. Nivolumab monotherapy may be continued at treating investigator discretion if there is evidence of clinical benefit. In this event, patient will continue nivolumab until AE is resolved and ipilimumab may be re-started or if ipilimumab is permanently discontinued (in congruence with guidelines in table below), then patient will continue nivolumab alone until cycles are completed. At completion of 4 cycles, patient may continue on nivolumab alone, as per protocol. If ipilimumab is permanently discontinued prior to receipt of 4 doses, nivolumab dosing should remain at the Cycle 1-4 dosing (1 mg/kg every 2 weeks) until completion of Cycle 4 and should then switch to Cycle 5+ dosing (480 mg every 4 weeks).

Table 8.1 Dose Modification for Related Adverse Events

Treatment-related Adverse Event	Grade of Event	Nivolumab and/or Ipilimumab
Nausea	≤ Grade 1	No dose modification
	Grade 2	Hold until ≤ Grade 1 OR baseline (exceptions as noted below) ¹
	Grade 3	Off protocol therapy (exceptions as noted below) ¹
	Grade 4	Off protocol therapy
*Patients requiring a delay of >2 weeks must go off protocol therapy.		
Recommended management: antiemetics.		
Diarrhea (immune-related enterocolitis)	≤ Grade 1	No dose modification

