Withhold ipilimumab and nivolumab dosing in patients symptomatic for hypophysitis. Initiate systemic corticosteroids at a dose of 1 to 2 mg/kg/day of prednisone or equivalent, and initiate appropriate hormone replacement therapy.

Other Immune-mediated Adverse Reactions, Including Ocular Manifestations

Ocular inflammation, manifested as Grade 2 or Grade 3 episcleritis or uveitis, was associated with concomitant diarrhea in a few patients (< 1%) and occasionally occurred in the absence of clinically apparent GI symptoms. Other presumed immune-related AEs reported include, but were not limited to, arthritis/arthralgias, pneumonitis, pancreatitis, autoimmune (aseptic) meningitis, autoimmune nephritis, pure red cell aplasia, noninfective myocarditis, polymyositis, and myasthenia gravis, of which were individually reported for < 1% of patients.

The following clinically significant immune-mediated adverse reactions were seen in less than 1% of ipilimumab-treated patients in Study 1: nephritis, pneumonitis, pulmonary granuloma resembling sarcoidosis, meningitis, pericarditis, uveitis, iritis, ITP, neutropenia and hemolytic anemia.

Across the clinical development program for ipilimumab, the following likely immune-mediated adverse reactions were also reported with less than 1% incidence: myocarditis, angiopathy, temporal arteritis, vasculitis, polymyalgia rheumatica, conjunctivitis, blepharitis, episcleritis, scleritis, leukocytoclastic vasculitis, erythema multiforme, psoriasis, pancreatitis, arthritis, and autoimmune thyroiditis.

Permanently discontinue ipilimumab and nivolumab for clinically significant or severe immune-mediated adverse reactions. Initiate systemic corticosteroids at a dose of 1 to 2 mg/kg/day prednisone or equivalent for severe immune-mediated adverse reactions.

Administer corticosteroid eye drops to patients who develop uveitis, iritis, or episcleritis. Permanently discontinue ipilimumab for immune-mediated ocular disease that is unresponsive to local immunosuppressive therapy.

- a. Overall, immune-related AEs commonly started within 3 to 10 weeks from first dose, were successfully managed in most instances by omitting doses, discontinuing dosing, and/or through administering symptomatic or immunosuppressive therapy, including corticosteroids, as mentioned above and detailed in [Section 7.0](#). Immune-related AEs generally resolved within days to weeks in the majority of patients

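### The 8.3b lead-in ends the Arm 1 ipilimumab restart window on Day 15, before dose 2 is due, and so contradicts the restart rules beneath it; bullet 3 also omits the Table 8.1 two-week limit

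*Combined protocol and SAP*

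**What the plan says.** Section 8.3 covers holding and restarting ipilimumab in Arm 1. Its opening sends event-specific rules to Table 8.1 ("Dose modifications for ipilimumab by adverse event type are detailed in" that table) and calls its own list general considerations.

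The restart rule in 8.3b begins: "Ipilimumab may be restarted if/when the adverse event(s) resolve(s) in severity or returns to baseline within 2 weeks of initial dose administration". Four bullets follow.

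- Bullet 1 concerns events that are unrelated to ipilimumab or not autoimmune or inflammatory. It requires discussion with the study chairs in this case: "If more than 1 dose is to be skipped or > 2 week delay is expected".
- Bullet 2 allows restart at the next scheduled timepoint once the event is Grade 1 or less, and tells sites to follow the guidelines for specific events.
- Bullet 3 reads "If the adverse event has not resolved in the protocol-specified dosing window" (3 weeks, plus or minus 3 days), "the next scheduled dose will be skipped and dosing will be resumed at the subsequently scheduled dose".
- Bullet 4 says that events needing steroids, other immunosuppressants, surgery or hormone replacement generally end treatment.

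Other limits also apply. Section 8.3c stops ipilimumab permanently for "Persistent adverse reactions that require holding more than 2 treatment doses". Section 8.3e permits delays to manage drug-related events. It also permits gaps of more than 6 weeks without ipilimumab for other reasons if the study chairs approve. Section 8.2b caps any delay at 84 days. In Table 8.1, the nausea, diarrhea, vomiting and neutropenia rows add: "Patients requiring a delay of >2 weeks must go off protocol therapy".

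**The concern.** The lead-in governs all four bullets, and its clock runs from the first dose rather than from the event or the held dose. That clock has run out before the first occasion on which a dose could be held. A site that follows the sentence literally would stop ipilimumab for any toxicity in cycles 2 to 4. A site that follows bullets 2 and 3 would continue.

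A second, smaller question is whether bullet 3's instruction to skip one dose and resume holds for the four event types that Table 8.1 limits to a two-week delay.

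What is at stake is consistent dosing in the control arm: the same event could end treatment at one site and not at another.

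**Working it through.** The plan gives no figure of its own here, so the check is calendar arithmetic and a comparison of the rules.

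**Inputs.** Arm 1 has 21-day cycles and four doses (7.2). The dosing window is plus or minus 3 days (8.3b, bullet 3). The lead-in limit is 14 days from the initial dose (8.3b). The Table 8.1 limit is 14 days in four rows. Up to 2 doses may be held (8.3c). The maximum delay is 84 days (8.2b).

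**Step 1: dates.**
- Scheduled doses: Days 1, 1 + 21 = 22, 22 + 21 = 43, 43 + 21 = 64.
- Lead-in limit: Day 1 + 14 = Day 15.
- Dose 2 window: 22 − 3 = Day 19 to 22 + 3 = Day 25.
- The limit falls 22 − 15 = 7 days before dose 2 is due, and 19 − 15 = 4 days before the earliest date on which it can be given.

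**Step 2: what each rule does with a Grade 2 non-skin event that is present on Day 22.**

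| Rule | Result |
|---|---|
| 8.3b lead-in | Deadline passed on Day 15; no restart |
| 8.3b bullet 2 | Restart at the next scheduled timepoint once Grade 1 or less; no calendar deadline |
| 8.3b bullet 3 | Unresolved in the window: skip Day 22, resume Day 43 |
| 8.3c | Two held doses (Days 22 and 43) tolerated; resuming on Day 64 is a delay of 64 − 22 = 42 days |
| 8.3e | Delay to manage a drug-related event is permitted |
| 8.2b | Delay of up to 84 days is permitted |

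The lead-in is the only rule that bars restart for this event, and it does so for every later event as well. Bullet 3 is the sharpest contradiction: it applies only to an event unresolved at Day 19 to 25, which has necessarily missed Day 15.

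**Step 3: bullet 3 against Table 8.1.** Take treatment-related Grade 2 nausea that starts on Day 22 and falls to Grade 1 on Day 40.
- Time from the held dose's scheduled date to resolution: 40 − 22 = 18 days, above 14.
- Time from that date to the next dose under bullet 3: 43 − 22 = 21 days, above 14.
- Bullet 3 resumes ipilimumab on Day 43. Table 8.1 takes the patient off protocol therapy, whichever way the delay is counted. None of the exceptions in the table's footnote 1 keeps this patient on treatment.

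**Step 4: how far step 3 extends.** If the same nausea resolves on Day 30, the time to resolution is 30 − 22 = 8 days, below 14, while the time to the next dose is still 21 days. Table 8.1 does not define delay, but the four rows are written as holds that end at Grade 1 or baseline. Time to resolution is therefore the natural meaning, and on that meaning the Day 30 case raises no conflict.

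**The case against.** The strongest reply is that the lead-in is a slip of wording that no careful site would apply. Bullet 1's mention of a two-week delay suggests that the authors meant two weeks from the held dose. Bullets 2 and 3, 8.3c, 8.3e and 8.2b all presuppose later restarts. This is persuasive about intent. It does not rescue the sentence, which sets a different limit in an operative dosing rule, and the protocol nowhere states the intended one.

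On Table 8.1, the reply is that precedence is already there: 8.3 defers to the table by event type, and bullet 2 points to event-specific guidelines. Most of this stands. What remains is a missing cross-reference in bullet 3.

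A reader might infer more than the documents support in four ways.

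- *Every bullet 3 skip breaches the two-week limit, because doses are 21 days apart.* This needs delay to mean time to the next dose, which is the less natural reading of those rows.
- *Events that resolve between Day 16 and Day 25 have no rule.* Bullet 2, taken on its own terms, covers them once they are Grade 1 or less.
- *Most immune-related events are shut out.* Section 8.7 does say: "Overall, immune-related AEs commonly started within 3 to 10 weeks from first dose, were successfully managed in most instances by omitting doses". That onset range is Day 1 + 21 = Day 22 to Day 1 + 70 = Day 71, all after Day 15. But bullet 4 generally ends treatment for events that need steroids, and 8.3c ends it for related Grade 3 or 4 events, with exceptions. Many such events would never reach the restart rule, and the documents do not give the split.
- *The PFS comparison is biased.* No hold or discontinuation rate is given for Arm 1, so nothing supports a direction or a size.

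**Conclusion.** The lead-in of 8.3b is wrong as written. Taken literally, it bars restart after any event that starts after Day 15 or is still present when dose 2 is due on Day 22, against bullets 2 and 3, 8.3c, 8.3e and 8.2b. The Table 8.1 point is real but minor: precedence is implied and not stated where bullet 3 gives the opposite instruction, and it concerns four treatment-related event types.

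The scope is Arm 1, 21 planned eligible patients (11.1), doses 2 to 4. The number of patients affected cannot be estimated. No effect on PFS, alpha, power or sample size is claimed.

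The conclusion takes the initial dose to be dose 1 on Day 1, with no earlier delay. The nausea example also assumes that no other stopping rule applies to that patient.

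**What to change.** 1. In the 8.3b lead-in, delete the last seven words, from *within* onward, and let the protocol's existing limits govern restart.
2. Add to bullet 3: *Where Table 8.1 sets a >2-week limit, counted from the scheduled date of the held dose to resolution to Grade 1 or less or baseline, that limit applies instead; otherwise the 8.3c limit of 2 held doses applies, with the study-chair discussion in bullet 1, the study-chair approval in 8.3e and the 84-day maximum in 8.2b unchanged.*

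The 8.3c limit fits inside the existing ceiling: two held doses give a delay of 42 days against 84. Resuming on Day 64 means 64 − 1 = 63 days since the last ipilimumab dose. That exceeds 6 weeks (42 days), which is why the 8.3e approval for non-drug-related gaps must stay in force.

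If the study chairs did intend a general two-week limit, they should keep it and re-anchor it to the scheduled date of the held dose. Bullet 3 would then need to say how it fits within that limit. The choice is a clinical one and the chairs should confirm it.

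The cost is one deletion and one sentence, with no new procedures, visits or patients.

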8.4 Dose Delay Criteria for Nivolumab in Combination with Ipilimumab (Arm 2)

Dose modifications for nivolumab in combination with ipilimumab by adverse event type are detailed in [Table 8.1](#). General considerations for dose modifications are as follows.

For the initial induction period, patients with Grade 2 or 3 events requiring discontinuation of treatment with the combination may consider continuing treatment with single agent nivolumab when the event resolves to baseline. However, patients with renal, CNS, or pulmonary toxicity must be removed from study.

- a. In addition to the AEs identified in the table below, ipilimumab and nivolumab dose should be delayed for any AE, laboratory abnormality or inter-current illness which, in the judgment of the treating investigator, warrants delaying the dose of study medication.
- b. Patients requiring a delay of > 6 weeks or who experience immune-related toxicity with inability to decrease prednisone ≤ 10 mg PO daily must go off protocol therapy entirely.
- c. Patients who received systemic corticosteroids for management of any drug-related immunologic toxicity must be off corticosteroids or have tapered down to an equivalent dose of prednisone 10 mg/day.
- d. Nivolumab monotherapy may be continued at treating investigator discretion if there is evidence of clinical benefit. In this event, patient will continue nivolumab until AE is resolved and ipilimumab may be re-started or if ipilimumab is permanently discontinued (in congruence with guidelines in table below), then patient will continue nivolumab alone until cycles are completed. At completion of 4 cycles, patient may continue on nivolumab alone, as per protocol. If ipilimumab is permanently discontinued prior to receipt of 4 doses, nivolumab dosing should remain at the Cycle 1-4 dosing (1 mg/kg every 2 weeks) until completion of Cycle 4 and should then switch to Cycle 5+ dosing (480 mg every 4 weeks).

Table 8.1 Dose Modification for Related Adverse Events

Treatment-related Adverse Event	Grade of Event	Nivolumab and/or Ipilimumab
Nausea	≤ Grade 1	No dose modification
	Grade 2	Hold until ≤ Grade 1 OR baseline (exceptions as noted below) ¹
	Grade 3	Off protocol therapy (exceptions as noted below) ¹
	Grade 4	Off protocol therapy
*Patients requiring a delay of >2 weeks must go off protocol therapy.		
Recommended management: antiemetics.		
Diarrhea (immune-related enterocolitis)	≤ Grade 1	No dose modification
	Grade 2	Hold until ≤ Grade 1 OR baseline (exceptions as noted below) ¹
	Grade 3	Off protocol therapy (exceptions as noted below) ¹
	Grade 4	Off protocol therapy
*Patients requiring a delay of >2 weeks must go off protocol therapy		

Recommended management: Loperamide antidiarrheal therapy Dosage schedule: 4 mg at first onset, followed by 2 mg with each loose motion until diarrhea-free for 12 hours (maximum dosage: 16 mg/24 hours) Adjunct anti-diarrheal therapy is permitted and should be recorded when used. See GI AE Algorithm for management of symptomatic colitis. Patients with Grade 2 symptoms but normal colonoscopy and biopsies may be retreated after resolution. Patients who require steroids must be taken off study treatment. Please evaluate pituitary function prior to starting steroids if possible without compromising acute care. Evaluation for all patients for additional causes includes C. diff, acute and self-limited infectious and foodborne illness, ischemic bowel, diverticulitis, and IBD.
		
Vomiting	≤ Grade 1	No dose modification
	Grade 2	Hold until ≤ Grade 1 OR baseline (exceptions as noted below) ¹
	Grade 3	Off protocol therapy (exceptions as noted below) ¹
	Grade 4	Off protocol therapy
*Patients requiring a delay of >2 weeks must go off protocol therapy.		
Recommended management: antiemetics.		
Other GI	≤ Grade 1	No dose modification
	Grade 2	Hold until ≤ Grade 1 OR baseline (exceptions as noted below) ¹
	Grade 3	Off protocol therapy (exceptions as noted below) ¹
	Grade 4	Off protocol therapy
Patients with Grade 2 or 3 N-V should be evaluated for upper GI inflammation and other immune related events.		
Neurologic events (new,	≤ Grade 1	No dose modification
	Grade 2	Hold until ≤ Grade 1 OR baseline (exceptions as noted below) ¹

Treatment-related Adverse Event	Grade of Event	Nivolumab and/or Ipilimumab
motor, sensory, encephalitis)	Grade 3	Off protocol therapy (exceptions as noted below) ¹
	Grade 4	Off protocol therapy
Fatigue	≤ Grade 1	No dose modification
	Grade 2	No dose modification
	≥Grade 3	Off protocol therapy (exceptions as noted below) ¹ – if fatigue is found related to endocrinopathy and clinical symptoms are managed with hormone replacement, patient resume therapy
	Grade 4	Off protocol therapy
Fatigue is the most common adverse event associated with immune checkpoint therapy. Grade 2 or greater fatigue should be evaluated for associated or underlying organ involvement including pituitary, thyroid, and hepatic, or muscle (CPK) inflammation		
Fever	≤ Grade 1	Evaluate and continue
	Grade 2	Hold until ≤ Grade 1.
Treatment-related Adverse Event	Grade of Event	Nivolumab and/or Ipilimumab
Fever (continued)	Grade 3	Hold until ≤ Grade 1.
	Grade 4	Off protocol therapy
Patients with fever should be evaluated as clinically appropriate. Patients may experience isolated fever during infusion reactions or up to several calendar days after infusion. Evaluation over the course of 1-2 weeks should be done for other autoimmune events that may present as fever		
Skin drug-related AE	≤ Grade 1	No dose modification
	Grade 2	Hold until ≤ Grade 1 OR baseline (exceptions as noted below) ¹
	Grade 3	Off protocol therapy (exceptions as noted below) ¹
	Grade 4	Off protocol therapy
*Patients with purpuric or bullous lesions must be evaluated for vasculitis, Steven-Johnson syndrome, TEN, and autoimmune bullous disease including oral lesions of bullous pemphigus/pemphagoid. Pruritus may occur with or without skin rash and should be treated symptomatically if there is no associated liver or GI toxicity. Note skin rash typically occurs early and may be followed by additional events particularly during steroids tapering. Recommended management: See AE management guidelines		
Pneumonitis, broncho-spasm, pulmonary toxicity or interstitial lung disease	≤ Grade 1	No dose modification. See Section 18.3 for Management recommendations.
	Grade 2	Hold dose pending evaluation. Resume after pulmonary and/or ID consultation excludes autoimmune related causes. Patient must be removed from protocol therapy if steroids are required
	Grade 3	Off protocol therapy
	Grade 4	Off protocol therapy

Treatment-related Adverse Event	Grade of Event	Nivolumab and/or Ipilimumab
Above does not include infusion reactions.		
Distinguishing inflammatory pneumonitis is often a diagnosis of exclusion for patients who do not respond to antibiotics and have no causal organism identified including influenza. Most patients with respiratory failure or hypoxia will be treated with steroids. Bronchoscopy may be required and analysis of lavage fluid for lymphocytic predominance may be helpful. Patients with new lung nodules should be evaluated for sarcoid like granuloma. Please consider recommending seasonal influenza killed vaccine for all patients. Recommended management: See Pulmonary Adverse Event Management Algorithm		
Thrombocytopenia	≤ Grade 1	No dose modification
	Grade 2	Hold until ≤ Grade 1 OR baseline (exceptions as noted below) ¹
	Grade 3	Off protocol therapy
	Grade 4	Off protocol therapy
Neutropenia	≤ Grade 1	No dose modification
	Grade 2	Hold until ≤ Grade 1 OR baseline (exceptions as noted below) ¹
	Grade 3	Off protocol therapy
	Grade 4	Off protocol therapy
*Patients requiring a delay of >2 weeks must go off protocol therapy.		
Renal	≤ Grade 1	No dose modification
	Grade 2	Hold until ≤ Grade 1.
	Grade 3	Off protocol therapy
	Grade 4	Off protocol therapy
See Section 18.3 for Management recommendations. ⁵		
Endocrine Hypophysitis Adrenal Insufficiency	≤ Grade 1	No dose modification
	Grade 2	Hold until patients are on a stable replacement hormone regimen. If treated with steroids patients must be stable off steroids for two weeks.
Treatment-related Adverse Event	Grade of Event	Nivolumab and/or Ipilimumab
Endocrine Hypophysitis Adrenal Insufficiency (continued)	Grade 3	Hold until patients are on a stable replacement hormone regimen. If treated with steroids patients must be stable off steroids for two weeks.
	Grade 4	Off protocol therapy
Note all patients with symptomatic pituitary enlargement, exclusive of hormone deficiency, but including severe headache or enlarged pituitary on MRI should be considered Grade 3 events. Isolated thyroid or testosterone deficiency may be treated as Grade 2 if there are no other associated deficiencies and adrenal function is monitored. Please evaluate pituitary function before beginning steroid therapy or replacement therapy of any kind. *Note patients with thyroiditis may be retreated on replacement therapy. Patients must be evaluated to rule out pituitary disease prior to initiating thyroid replacement.		

Treatment-related Adverse Event	Grade of Event	Nivolumab and/or Ipilimumab
Recommended management: See Endocrine Management Algorithm		
Abnormal liver function (AST/ALT, Total bilirubin, immune-related hepatitis)	≤ Grade 1	No dose modification
	Grade 2	Hold until ≤ Grade 1 OR baseline (exceptions as noted below) ¹
	Grade 3	Off protocol therapy
	Grade 4	Off protocol therapy
Continued treatment of active immune mediated hepatitis may exacerbate ongoing inflammation. Holding drug to evaluate LFT changes and early treatment are recommended. LFT changes may occur during steroid tapers from other events and may occur together with other GI events including cholecystitis/pancreatitis.		
Recommended management: see Hepatic AE management algorithm		
Amylase or lipase, associated with GI symptoms	≤ Grade 1	No dose modification
	Grade 2	Hold until ≤ Grade 1 OR baseline (exceptions as noted below) ¹
	Grade 3	Hold until baseline and asymptomatic. Patients who develop symptomatic pancreatitis or DM must be taken off treatment ⁵
	Grade 4	Off protocol therapy
Patients may develop symptomatic and radiologic evidence of pancreatitis as well as DM and DKA. Lipase elevation may occur during the period of steroid withdrawal and with other immune mediated events or associated with colitis, hepatitis, and patients who have asymptomatic lipase elevation typically have self-limited course and may be retreated. For treatment management of symptomatic pancreatitis please follow the Hepatic Adverse Event Management Algorithm		
Any other laboratory abnormality (except AST/ALT, Total bilirubin, thrombocytopenia, neutropenia, lymphopenia)	≤ Grade 1	No change.
	Grade 2	No change.
	Grade 3	Off protocol therapy unless is unrelated to underlying organ pathology and can be managed with electrolyte replacement, hormone replacement, insulin, or no therapy
	Grade 4	Off protocol therapy unless is unrelated to underlying organ pathology and can be managed with electrolyte replacement, hormone replacement, insulin, or no therapy
	² Grade 4 lymphopenia or leukopenia or does not require drug discontinuation. ³ Isolated Grade 4 electrolyte imbalances/abnormalities that are not associated with clinical sequelae and are corrected with supplementation/appropriate management within 72 hours of their onset do not require drug discontinuation. ⁴ Resolved, well-controlled, or asymptomatic hypothyroidism does not require approval by Study	

Treatment-related Adverse Event	Grade of Event	Nivolumab and/or Ipilimumab
		Chairs prior to restarting therapy.
Treatment-related Adverse Event	Grade of Event	Nivolumab and/or Ipilimumab
Cardiac*	≤ Grade 1	Hold dose pending evaluation and observation.** Evaluate for signs and symptoms of CHF, ischemia, arrhythmia or myositis. Obtain history EKG, CK (for concomitant myositis), CK-MB. Repeat troponin, CK and EKG 2-3 calendar days. If troponin and labs normalize may resume therapy. If labs worsen or symptoms develop then treat as below. Hold pending evaluation.
	Grade ≥2 with suspected myocarditis	Hold dose.** Admit to hospital. Cardiology consult. Rule out MI and other causes of cardiac disease. Cardiac Monitoring. Cardiac Echo. Consider cardiac MRI and cardiac biopsy. Initiate high dose methylprednisolone. If no improvement within 24 hours, add either infliximab, ATG or tacrolimus. Resume therapy if there is a return to baseline and myocarditis is excluded or considered unlikely.
	Grade ≥2 with confirmed myocarditis	Off protocol therapy. Admit to CCU (consider transfer to nearest Cardiac Transplant Unit). Treat as above. Consider high dose methylprednisolone. Add ATG or tacrolimus if no improvement. Off treatment.

*Including CHF, LV systolic dysfunction, Myocarditis, CPK, and troponin **Patients with evidence of myositis without myocarditis may be treated according as "other event" Note: The optimal treatment regimen for immune mediated myocarditis has not been established. Since this toxicity has caused patient deaths, an aggressive approach is recommended.
		
Infusion Reaction	≤ Grade 1	No dose modification
	Grade 2	Interrupt study drug. Upon recovery from symptoms, resume study drug at one half the initial infusion rate, then increase incrementally to the initial infusion rate
	Grade 3	Off protocol therapy
	Grade 4	Off protocol therapy

Patients with fever should be evaluated as clinically appropriate. Patients may experience isolated fever during infusion reactions or up to several calendar days after infusion. Evaluation over the course of 1-2 weeks should be done for other autoimmune events that may present as fever
		
All other events	≤ Grade 1	No dose modification

Treatment-related Adverse Event	Grade of Event	Nivolumab and/or Ipilimumab
	Grade 2	Hold until \leq Grade 1 OR baseline(exceptions as noted below) ¹
	Grade 3	Off protocol therapy
	Grade 4	Off protocol therapy

Table 8.1 Footnotes

¹Recommended management: As clinically indicated

Exceptions:

- Any Grade 2 drug-related uveitis or eye pain or blurred vision that does not respond to topical therapy and does not improve to Grade 1 severity within the re-treatment period OR requires systemic treatment must go off protocol treatment
- Any adverse event, laboratory abnormality, or intercurrent illness which, in the judgment of the treating investigator, presents a substantial clinical risk to the patient with continued study drug dosing must go off protocol treatment.
- Any Grade 3 or 4 drug-related laboratory abnormality or electrolyte abnormality, that can be managed independently from underlying organ pathology with electrolyte replacement, hormone replacement, insulin or that does not require treatment does not require discontinuation.

⁵ Recommended management: As clinically indicated

- See [Section 18.3](#) for recommended management
- See [Section 8.4](#) for treatment management

